The here proposed study, conducted in patients undergoing surgery, aims to 1) describe the incidence and types of postoperative pulmonary complications (PPCs), 2) describe patient demographics, baseline characteristics, and intraoperative ventilation management, 3) describe the occurrence of intraoperative adverse events (IAEs), and 4) their associations with PPCs, and 5) assess the practice of intraoperative mechanical ventilation.

Study design

This is an observational investigator–initiated, international, multicenter, prospective, cross–sectional study.

Local investigators will capture data in an electronic CRF (eCRF), including patient demographics and baseline characteristics, intraoperative ventilator settings and ventilation parameters, and outcomes.

Study population

Patients are eligible for participation if: 1) adult and 2) receiving intraoperative ventilation during general anesthesia for surgery. We will exclude patients receiving ventilation outside of an operating room as well as patients receiving intraoperative ventilation during extracorporeal life support.

Main study endpoints

The primary endpoint is to report the number of patients with PPCs occurring in the first 5 postoperative days. As secondary endpoint, the practice of mechanical ventilation in patients undergoing general anesthesia for surgery will be ascertained including key intraoperative ventilator characteristics and respiratory system mechanics. Other secondary endpoints will include: incidence and type of IAEs; postoperative complications other than PPCs in the first 5 postoperative days; impact of intraoperative hemodynamic management on the occurrence of

PPCs, intensive care unit (ICU) admission and length of stay, hospital length of stay, and hospital mortality on day 28.

Study duration

The overall duration of the study is 18 months, with 9 months allocated for enrollment and data collection, and 9 months dedicated to statistical analysis.

Participating hospitals have to prospectively collect data in a consecutive manner within a predefined period of 1 week (7 days). Also, participating hospitals can decide on which period they choose to collect data, but data collection must take place during a predetermined time window of 8 weeks, following the ethical committee/internal review board approval.

Nature and extent of the burden and risks associated with participation, benefit and group relatedness

Prospective collection of demographic data, ventilation settings and ventilation parameters, and outcomes means the risks are negligible and the burden is minimal.

Data collection

- Informed consent and data of admission
- Demographic and clinical characteristics
- Characteristics of the surgical procedure (elective vs non-elective, cardiac vs non-cardiac, open vs minimally invasive)
- The type of anesthesia (involving volatile anesthetic medications or intravenous agents)
- Mechanical ventilation settings and respiratory system mechanics variables
- Monitored parameters (peripheral oxygen saturation, end-tidal carbon dioxide tension, arterial blood gases if available, mean blood pressure, systolic and diastolic blood pressure, and heart rate)
- Extubation procedure
- Peri- and postoperative variables and outcomes
- Follow up to the fifth postoperative day
- In-hospital death and hospital length of stay on 28th day after surgery.

Sample size

Considering a PPCs incidence around 10% as found in previous research, at least 10000 patients are needed to achieve a confidence interval width of 0.0119.

Statistical analysis

Variables will be reported as mean and standard deviation or median and interquartile

range according to the normal or non-normal distribution. Also, the comparisons among variables will be carried out through student T-test or Mann- Whitney U test according to data distribution. As regards as categorical variables, proportions will be reported and comparisons will be performed by the Chi-square or Fisher exact test as appropriate. The following planned secondary analyses will be carried out:

- Cardiac vs non-cardiac surgery
- Elective vs non-elective procedures
- Practice of weaning from invasive mechanical ventilation
- Open vs minimally invasive/robotic surgery
- Comparison among the different obesity classes
- Obese vs non obese patients
- Impact of geo-economical difference

1. RATIONALE

1.1. Practice of intraoperative mechanical ventilation

Ventilation during surgery carries potential risks for patients receiving general anesthesia (1). Postoperative pulmonary complications (PPCs) have been described to occur in up to 4% of general surgical cases (2). Nevertheless, patients at an elevated risk for PPCs have reported significantly higher incidence rates (3-7). PPCs are intricately tied to heightened degrees of both morbidity and mortality, even when PPCs are mild (8). In general surgery population (4) and surgical patients undergoing minimally invasive procedures (9), it has been demonstrated that specific ventilator settings impact the onset of PPCs. Since these two studies (4,8), numerous randomized clinical trials focused on the intraoperative ventilation regulation have investigated the impact of ventilator settings on PPCs in patients undergoing major surgery (9-10), abdominal surgery (6,11-13), or thoracic surgery (14-15). In addition, several systematic reviews and meta-analysis have been performed and published (2,16-19). The findings from these studies and meta-analyses may have significantly influenced ventilator management in these patient groups. Concurrently, evolving surgical practices favor minimally invasive procedures over open surgery, particularly in abdominal surgeries where deep Trendelenburg positioning can substantially affect ventilatory characteristics (20). As experience and knowledge about intraoperative ventilation in these challenging scenarios proliferate within medical communities, this evolving understanding is even translating into updated guidelines (21-23).

1.2. Need for a study

A new worldwide study is needed with the aim of ascertaining how patients are ventilated during general anesthesia for surgery. This study will help us understand how intraoperative ventilation is currently managed in general patients population and specific patients groups. It will also shed the light on risk factors that currently have associations with PPCs and, finally, with poor clinical outcomes. This information can help in deciding which ventilation strategies should be tested in future randomized clinical trials of intraoperative ventilation, and will inform trialists on sample size calculations of such studies.

2. HYPOTHESYS AND OBJECTIVES

2.1. Study hypothesis

PPCs incidence is high and related to patient and surgery characteristics. The key mechanical ventilator regulations during general anesthesia for surgery are independently associated with PPCs incidence. Finally, postoperative outcomes is strongly conditioned by PPCs occurrence.

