5. METHODS

5.1. Study Outcome

5.1.1. Primary outcome

The primary endpoint is to report the number of patients with PPCs, considered as a composite incidence of predefined postoperative pulmonary complications occurring in the first 5 postoperative days or hospital discharge whichever comes first, examining also individual PPCs incidence and type (for the definitions of PPCs see '11').

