5.1.2. Secondary outcomes

Secondary endpoints include: 1) ascertaining the practice of mechanical ventilation in patients undergoing general anesthesia for surgery including key intraoperative ventilator characteristics and respiratory system mechanics; 2) describing the incidence and type of IAEs; 3) describing postoperative complications other than PPCs in the first 5 postoperative days or hospital discharge whichever comes first; 4) describing the impact of intraoperative hemodynamic management on the occurrence of PPCs; 5) reporting intensive care unit (ICU) admission and length of stay, hospital length of stay, and hospital mortality on day 28.

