Weaning phase: at beginning and at the end of weaning phase, the following variables will be acquired: ventilatory mode, Vt (ml), PEEP (cmH₂O), pressure support over PEEP (if any) (cmH₂O), inspiratory trigger regulations, FiO₂, respiratory rate (breaths/min), SpO₂ (%), EtCO₂(mmHg or kPa), mean, systolic, and diastolic arterial pressure (either invasive or non-invasive), mmHg, heart rate (beats per minute).

It will also be recorded if aspiration is performed prior to tube removal. The number and type of IAEs will be acquired throughout the whole duration of surgical and anesthesiologic procedures (see "11" for definitions).

Peri-operative variables: duration of anesthesia procedure, duration of surgical procedure, tube type and size, type of anesthesia, type of analgesia (total endovenous, antibiotic prophylaxis, details on neuromuscular function monitoring and about the use of reversal agents (if any), total intra-operative fluid and total transfusion of blood products, temperature and hemoglobin at end of surgery (if clinically available). The possible admission to post-anesthesia care unit (PACU) and the eventual administration of non-invasive respiratory support (NIRS), namely, high flow oxygen therapy, continuous positive airway pressure, and non-invasive bilevel positive airway pressure ventilation, and the settings will be recorded.

Post-operative variables: vital signs involving SpO₂, heart rate, systolic, diastolic, and mean arterial pressure, body temperature if assessed, eventual arrythmias occurrence, and the blood gas analysis parameters (optional assessment) will be hourly collected in the immediate post-operative period or PACU stay, and at the discharge to surgical ward or ICU.

Follow up (day 0 to 5): PPCs are recorded from the medical chart on day 0 (end of surgery to 23:59h) and on days 1,2,3,4 and 5 post-operative (each day runs from 00:00 AM to 23:59 PM). Follow–up is completed on the day of discharge or on day 5 if the patient is still admitted.

On day 0 the following variables are collected: IMV after discharge from the operation room, admission to ICU/PACU after surgery, PPCs (see "11").

On day 1,2,3,4 and 5 the following variables will be collected: any new admission to ICU; any new or prolonged IMV; PPCs (see "11").

The data mentioned above are considered essential to defined as "complete" each patient's medical record.

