ICU or PACU admission: recording of data during the critical care submission can be left out by the participating centers if this workload exceeds their possibilities. However, it is requested to collect the ICU/PACU data. In case of IMV and/or admission to the ICU/PACU during the follow-up period (day 0, 1, 2, 3, 4 or 5), the following variables will be collected on a different CRF: reason for ICU/PACU admission, reason for IMV or NIRS, APACHE II score (24), on (first) admission to and within the first 24 hours in ICU (i.e., the APACHE II score to be collected and reported for patients who were in the ICU before surgery, and were referred to the ICU after surgery, starts direct after the first admission to the ICU; the APACHE II score to be collected and reported for patients who were not in the ICU before surgery, but were referred to the ICU after surgery, starts direct after surgery, in the ICU). At the first hour of ICU/PACU admission and in case of continued admission each day (during morning rounds) the following variables are collected: SOFA score, IMV regulations, arterial blood gas values (pH, PaCO₂, PaO₂ if available), closest to 08:00 AM, PPCs (number and type, see "p 11"), extra-pulmonary organ failure (number and type), and risk factors for respiratory failure (number and type).

If a patient is transferred back to the ward, the non–ICU/PACU follow–up CRF will be used to record the variables of the remaining follow–up days.

Follow up (day 28): On day 28 ICU and hospital length of stay as well as in hospital death are assessed.

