6. STATISTICAL ANALYSIS

The demographic and baseline characteristics of the study population will be reported. Continuous variables will be summarized using median and interquartile range (IQR), and categorical variables will be summarized using frequencies and percentages. The comparison among groups for categorical variables will be performed by considering the Chi-square test or Fisher's exact test whatever is appropriate; for continuous variables, the Wilcoxon -Rank Sum test will be used.

The primary endpoint, namely, the PPCs rate, will be calculated together with the 95% confidence interval (CI). Moreover, the impact of the patient's characteristics on the risk of PPCs will be handled by using appropriate statistical models, such as Logistic Regression. These analyses will be adjusted for potential confounders identified at the study's outset, providing insights into factors that may influence PPCs rates among the patients population subjected to surgery. The 95% CIs on the model OR (Odds Ratios) and predicted probability of PPCs, according to the patient's profile, will be estimated. Handling of missing data will be addressed through robust methods like multiple imputation or complete case analysis, depending on the nature and extent of the missingness. Sensitivity analyses will further assess the robustness of the findings, examining how different assumptions about the missing data and analytical methods influence the results.

The significance of differences will be defined by the p-values, with a value of less than 0.05 considered statistically significant.

The following planned secondary analyses will be performed:

- Cardiac vs non-cardiac surgery
- Elective vs non-elective procedures
- Obese vs non-obese patients
- Open vs minimally invasive/robotic surgery

- Comparison among the different obesity classes
- Practice of weaning from invasive mechanical ventilation
- Impact of geo-economical difference

The analyses will be performed by using R 3.4.2.

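### If hospital stay is compared by eventual PPC status with the fixed-group tests that Section 6 names, time in hospital before the PPC biases the result towards a longer stay, even when PPCs have no effect

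*Protocol*

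**What the plan says.** Section 2.1 makes PPC the exposure in its third hypothesis: "postoperative outcomes is strongly conditioned by PPCs occurrence". The outcomes available to examine it are in Section 5.1.2 ("reporting intensive care unit (ICU) admission and length of stay, hospital length of stay, and hospital mortality on day 28") and in the day-28 follow-up of Section 5.2 ("On day 28 ICU and hospital length of stay as well as in hospital death are assessed").

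The window in which a PPC can be recorded closes at discharge. Section 5.1.1 counts complications "occurring in the first 5 postoperative days or hospital discharge whichever comes first", and Section 5.2 says that follow-up is "completed on the day of discharge or on day 5 if the patient is still admitted". Within that window the calendar day is known: "PPCs are recorded from the medical chart on day 0 (end of surgery to 23:59h) and on days 1,2,3,4 and 5 post-operative".

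For comparisons between groups, Section 6 names chi-square or Fisher for categorical data and, "for continuous variables, the Wilcoxon -Rank Sum test will be used". The Summary names the t-test or Mann-Whitney test instead, which are also fixed-group tests. The only model described is logistic regression with PPC as the outcome. Neither the objectives in Section 2.2 nor the seven secondary analyses in Section 6 include a comparison of outcomes by PPC status.

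**The concern.** PPC status is not known at the end of surgery. A patient whose first PPC appears on day 4 must still have been in hospital on day 4. A patient discharged on day 1 can have a PPC recorded only on day 0 or 1. Sorting patients by whether they ever had a PPC therefore sorts them partly by stay, and the days before the PPC are counted as stay belonging to the PPC group. This is immortal-time bias: the exposed group is guaranteed the time it needed to become exposed.

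At stake is the third hypothesis. With about 10,000 patients, a gap of half a day produced by this mechanism alone can be highly significant and could be read as support for the claim that PPCs prolong stay.

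**Working it through.** **The plan's own figure.** With 1,000 events in 10,000, the 95% Clopper-Pearson limits are 0.09419 and 0.10605. The width is 0.10605 − 0.09419 = 0.01186, which agrees with the stated 0.0119. This point does not touch that figure.

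**Inputs.** From the protocol: PPC rate 10% and N = 10,000 (Section 4.4), and a PPC window of day 0 to the earlier of discharge and day 5 (Sections 5.1.1 and 5.2). Assumed, because the protocol gives neither: the distribution of stay and the share of PPCs on day 0. In every calculation below, PPC has no effect on stay.

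**Step 1, by hand.** Half the patients leave on day 1 and half on day 6. Everyone in hospital has a 3% chance of a first PPC each day, from day 0 to day 5.
- P(PPC), leaving on day 1 (two days at risk): 1 − 0.97² = 0.0591.
- P(PPC), leaving on day 6 (six days at risk): 1 − 0.97⁶ = 0.1670.
- Overall rate: (0.0591 + 0.1670)/2 = 0.113.
- Mean stay with PPC: (0.0591×1 + 0.1670×6)/(0.0591 + 0.1670) = 4.69 days.
- Mean stay without PPC: (0.9409×1 + 0.8330×6)/(0.9409 + 0.8330) = 3.35 days.

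The gap is 1.34 days with no effect at all. Under a landmark at the end of day 1, only the day-6 leavers remain. Each has 5 days to go whatever the PPC status, so the gap is 0.

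**Step 2, simulation with hazard spread over days 0 to 5.** Stay is log-normal, rounded down (log-SD 0.8 in the cases shown). The daily PPC hazard is the same for all in-patients and scaled to a 10% rate.

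| Hazard by day | Median stay | Mean stay, PPC vs none | Gap |
|---|---|---|---|
| constant | 3 | 5.5 vs 4.1 | 1.4 |
| constant | 1 | 2.5 vs 1.5 | 1.0 |
| weights 3,3,2,1,1,1 | 3 | 5.0 vs 4.2 | 0.8 |
| weights 3,3,2,1,1,1 | 1 | 2.2 vs 1.5 | 0.7 |

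The rank-sum p-value at n = 10,000 was below 1e-7 in all 16 scenarios of this kind. Those scenarios put only about 23% to 50% of PPCs on day 0.

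**Step 3, varying the day-0 share.** The rest of the PPCs arise at a constant hazard over days 1 to 5. There were 60 replicates of 10,000 patients per cell. Entries are the spurious gap in mean stay (days), with the rank-sum rejection rate at 0.05.

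| Stay before rounding down (median, log-SD) | 25% on day 0 | 50% | 75% | 90% | 100% (gap only) |
|---|---|---|---|---|---|
| 1.5, 1.0 | 2.10 (100%) | 1.43 (100%) | 0.71 (100%) | 0.31 (93%) | 0.01 |
| 3, 0.8 | 1.45 (100%) | 0.98 (100%) | 0.50 (100%) | 0.21 (50%) | −0.02 |
| 5, 0.8 | 1.28 (100%) | 0.90 (100%) | 0.47 (90%) | 0.25 (32%) | 0.03 |
| 5, 0.4 | 0.37 (100%) | 0.23 (97%) | 0.14 (50%) | 0.03 (15%) | −0.01 |

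The direction is the same whenever some PPCs arise after day 0 and some patients leave before day 5. The size shrinks as PPCs concentrate on day 0 and as stay becomes more uniform. A separate run of the null case gave +0.7 to +1.4 days with 100% rejection at about 26% to 50% on day 0, and 0.1 to 0.2 day with 37% to 62% rejection at about 88% to 94%.

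**Step 4, the same kind of null data with timing respected.** With PPC as a time-dependent exposure, the pooled daily odds ratio for discharge was 0.99 to 1.01, and rejection averaged about 5% (0% to 13% by cell, which is noise at 60 replicates). A landmark at the end of day 1 rejected in about 5% to 7% of replicates. The spurious effect disappears.

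**The case against.** The strongest reply is that the protocol contains no such analysis. Section 2.1 fixes no exposure definition or test, Section 5.1.2 only reports stay and mortality, and none of the planned secondary analyses is by PPC status. The rank-sum sentence stands in a paragraph that opens with baseline characteristics and refers to unspecified groups. A statistical analysis plan, not seen here, could treat PPC as time-dependent. All of this is correct, and it makes the point conditional. It does not remove it: the protocol states the hypothesis, closes the exposure window at discharge, and offers no between-group method except fixed-group tests.

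The second reply is that the size is unknown. This also stands. Section 11.1 counts unplanned oxygen and prolonged ventilation from the day of surgery, so PPCs may cluster on day 0. If about 90% do, the gap is a fraction of a day, which would hardly support an effect described as strong.

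A reader might go further than the documents allow in three ways:
- **Early death biases in the opposite direction.** Nothing in the protocol, and no calculation here, establishes this.
- **Non-invasive support entails ICU care, so the ICU association is built in.** Section 5.2 records such support in the PACU and Section 11.1 includes high-flow oxygen. Neither ties it to ICU admission.
- **Only ICU admissions on a day after the PPC should count.** That would discard same-day admissions which a PPC had caused.

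**Conclusion.** The concern holds in conditional form. Applied to the third hypothesis, the only group-comparison methods that the protocol names would give an answer on length of stay that is biased towards the hypothesis. Under the assumed stay distributions and a 10% PPC rate, the spurious gap is about 0.7 to 1.4 days with roughly a quarter to a half of PPCs on day 0, about 0.1 to 0.2 day with about 90%, and none with all on day 0. Other stay shapes widen this: at 25% to 50% on day 0 the table runs from 0.23 to 2.10 days. The calculations isolate this one mechanism and leave out confounding by severity.

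A reader might infer that the protocol commits itself to treating PPC as a fixed group, or that the hypothesis will be confirmed whether or not it is true. The documents support neither: no PPC-versus-stay analysis is written, and the size depends on timing that they do not give. The primary PPC rate and its precision are unaffected.

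**What to change.** Add to Section 6 that, for the third hypothesis in Section 2.1:
- PPC is analysed as a time-dependent exposure using the recorded PPC day. Alternatively, a landmark analysis takes patients still in hospital at the end of day 1 (repeated at days 2 and 3), groups them by PPC status by then, and uses remaining stay and later in-hospital death to day 28 as outcomes.
- Any fixed-group comparison of total stay by eventual PPC status is descriptive only.
- ICU admission by PPC status is reported descriptively, noting that a PPC and an ICU admission on the same day cannot be ordered.

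**Cost.** No new variable is needed for PPC timing, since Section 5.2 already says "On day 1,2,3,4 and 5 the following variables will be collected: any new admission to ICU; any new or prolonged IMV; PPCs". There are four limits:
- The landmark excludes patients discharged before it and ignores later PPCs.
- In-hospital death is assessed on day 28, so its date must be taken from length of stay.
- Section 5.2 lets centres omit critical-care data. The PPC day should be kept for ICU patients even where the rest of that form is left out.
- The reported effect of PPCs on stay will be smaller than a fixed-group comparison would show.

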2.2. Study objectives

- To describe the incidence and type of PPCs in the first 5 postoperative days;
- To describe associations of patient, surgery, and intraoperative ventilation characteristics with the occurrence of PPCs;
- To describe the impact of intraoperative hemodynamic management on the occurrence of PPCs;
- To describe the occurrence of intraoperative adverse events (IAEs); and
- To describe geo
 economic differences in intraoperative ventilation management.

3. STUDY DESIGN

This is an observational investigator-initiated, international, multicenter, prospective, cross-sectional study recruiting academic and non-academic centers.

